## **4. TREATMENTS**

### **4.1 INVESTIGATIONAL TREATMENTS**

The investigational product BI 894416 as tablet formulation has been manufactured by BI Pharma GmbH & Co. KG. Rifampicin tablets will be obtained from a public pharmacy by the trial site.

#### **4.1.1 Identity of the Investigational Medicinal Products**

The characteristics of the test product are given below:

##### Test product 1:

Substance: BI 894416  
Pharmaceutical formulation: Tablet  
Source: BI Pharma GmbH & Co. KG, Germany  
Unit strength: 25 mg  
Posology: 2-0-0  
Route of administration: oral  
Duration of use: 1 day (in treatment periods 1 and 2)

##### Test product 2:

Name: Eremfat® 600 mg  
Substance: Rifampicin  
Pharmaceutical formulation: Film-coated tablet  
Source: Public pharmacy (obtained by the site)  
Holder of marketing authorization:  
Unit strength: 600 mg  
Posology: 0-0-1  
Route of administration: oral  
Duration of use: 7 days (Days -7 to -1 in treatment period 2)

#### **4.1.2 Selection of doses in the trial**

##### Perpetrator (rifampicin)

Rifampicin given at a dosage of 600 mg once daily reflects standard clinical doses and is considered sufficient to yield significant CYP3A induction.

### Victim (BI 894416)

Based on in vitro data, CYP3A is major responsible enzyme for metabolism of BI 894416. Additionally, BI 894416 was determined to be a substrate of CYP1A1, an extrahepatic enzyme expressed in tissues such as lung and small intestine. Concomitant administration of BI 894416 with the strong CYP3A inducer rifampicin may result in reduction of BI 894416 plasma concentrations. It is not expected that plasma concentrations of BI 894416 could increase when given together with rifampicin in this trial, in particular because of the interval of 14 hours between last administration of rifampicin on Day -1 of period 2 and the following administration of BI 894416 on Day 1 of period 2. This time interval of 14 hours makes any inhibitory effects of rifampicin that could potentially increase plasma concentrations of BI 894416, such as inhibition of intestinal P-glycoprotein, unlikely.

For the current trial, a dose of 50 mg BI 894416 is selected.

see IB [c03536505-04](#)), and it is in the range of doses that were given in first-in-man trial 1371-0001 to healthy volunteers and that were associated with good safety and tolerability.

In the SRD part of trial 1371-0001, single oral doses of 3 to 70 mg BI 894416 were given as oral solution formulation under fasting conditions, and available data indicate that, at all doses tested, BI 894416 administration was safe and well tolerated. In the 70 mg dose group of trial 1371-0001, gMean values for  $C_{max}$  and  $AUC_{0-24}$  of 2130 nM and 11100 nM\*h, respectively, were reached [c03536505-04]. In the 54 mg dose group of trial 1371-0001, gMean values for  $C_{max}$  and  $AUC_{0-24}$  of 1240 nM and 6940 nM\*h, respectively, were reached [c03536505-04]. I.e., the ratios of gMean plasma exposure parameters at 70 mg and at 54 mg were approximately 1.7 ( $C_{max}$ ) and 1.6 ( $AUC_{0-24}$ ). These ratios are assessed to be sufficient as safety margins for the current trial, in particular as a decrease of BI 894416 plasma concentrations is expected when given with rifampicin.

#### **4.1.3      Method of assigning subjects to treatment groups**

There is only one treatment sequence investigated in this trial, and each subject will be allocated to the same treatment sequence (R-T). The subjects will be allocated to a study subject number by the method 'first come - first served' prior to first administration of trial medication in the morning of Day 1 of Visit 2. Reference and test treatments will be administered in the sequence specified in the [Flow Chart](#).

Once a subject number has been assigned, it cannot be reassigned to any other subject.

The application of single BI 894416 doses of up to 70 mg (1371-0001) was well tolerated. For details on these results, refer to Sections [1.4.3](#) and [4.1.2](#) of the protocol.

Two possible interactions are known for rifampicin: (1) it causes induction of CYP3A4 and would therefore lead to a decreased BI 894416 exposure, and (2) it can interact with drug transporters which might lead to an increase BI 894416 exposure. By applying rifampicin in the evening and dosing BI 894416 at the next morning (refer to flow chart), an increase of BI 894416 exposure is not expected. Therefore, this dose regime is used in this study and an

Proprietary confidential information © 2019 Boehringer Ingelheim International GmbH or one or more of its affiliated companies

unexpected increase of BI 894416 exposure, beyond the exposure tested in the preceding study 1371-0001, is unlikely.

Thus, there should be no undue risk for a subject participating in this study. In addition, it is considered an acceptable option that an entire cohort of up to 16 subjects may be dosed on one day, due to (1) the seen good tolerability of up to 70 mg in the SRD study and (2) the application of 50 mg (below the highest tested dose in study 1371-0001) with an expected lower exposure after CYP 3A4 induction.

#### 4.1.4 Drug assignment and administration of doses for each subject

This trial is a one-way crossover study. All subjects will receive the 2 treatments in fixed order. The treatments to be evaluated are outlined in Table [4.1.4: 1](#) below.

Table 4.1.4: 1 Dosage and treatment schedule

Treatment period	Treatment	Substance	Formulation	Unit strength	Dosage	Total dose
1	R (Reference)	BI 894416	Tablet	25 mg	2 tablets as single dose on Day 1	50 mg
2	T (Test)	Rifampicin	Film-coated tablet	600 mg	1 tablet q.d on Days -7 to -1	4200 mg
		BI 894416	Tablet	25 mg	2 tablets as single dose on Day 1	50 mg

Administration of BI 894416 will be performed after subjects have fasted overnight; fasting is to start no later than 10 h before the scheduled dosing.

For administrations of rifampicin, subjects are advised to fast for at least 2 hours before and at least 30 minutes after drug administrations.

The investigator (or authorised designee) will administer the trial medication as an oral dose together with about 240 mL of water to subjects who are in a standing position. For drug administration, the so-called four-eye principle (two-person rule) should be applied. For this, one authorised employee of the trial site should witness the administration of trial medication, and – if applicable – its preparation (e.g. reconstitution), if correct dosage cannot be ensured otherwise.

For restrictions with regard to diet, see Section [4.2.2.2](#).

Subjects will be kept under close medical surveillance until 24 h after BI 894416 administration. During the first 4 h after BI 894416 administration, subjects are not allowed to lie down (i.e. no declination of the upper body of more than 45 degrees from upright posture).

The first rifampicin administration will be followed by a 2-hour post-administration in-house observation period.

The administrations of BI 894416 will be separated by a wash-out phase of at least 10 days.

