## FLOW CHART

Period	Visit	Day	Planned time (relative to BI 894416 administration) [h:min]	Approximate clock time of actual day [h:min]	Event and comment	Safety laboratory 	PK blood BI 894416	PK blood rifampicin	PK urine BI 894416 	12-lead ECG	Neurological examination 	Vital signs (BP, PR)	Questioning for AEs and concomitant therapy 
SCR	1	-21 to -2			Screening (SCR) 	A				x	x	x	
1 (BI 894416 alone)	2	1	-1	-14:00	18:00	Admission to trial site	x 						
			1	-2:00	06:00	Allocation to study subject numbers 	B 	x 	x 	x 		x 	x 
				0:00	08:00	BI 894416 administration			▲				
				0:15	08:15		x						
				0:30	08:30		x						
				0:45	08:45		x						
				1:00	09:00		x			x		x	
				1:30	09:30		x						
				2:00	10:00	240 mL fluid intake	x		x	x	x	x	
				2:30	10:30		x						
				3:00	11:00		x						
				4:00	12:00	240 mL fluid intake, thereafter lunch 	x	+				x	
				6:00	14:00		x						
				8:00	16:00	Snack (voluntary) 	x	+					
				10:00	18:00		x						
				11:00	19:00	Dinner							
				12:00	20:00		x	+			x		
			2	24:00	08:00	Discharge from trial site, breakfast  (voluntary)	B	x	▼	x	x	x	
				34:00	18:00	Ambulatory visit		x				x	
			3	48:00	08:00	Ambulatory visit		x				x	
2 (BI 894416 + rifampicin)	3	-7	-158:30	17:30	Admission to trial site 	x 						x 	
				-158:00	18:00	Rifampicin administration							
				-157:00	19:00	Dinner							
				-156:00	20:00	Discharge from trial site						x	
		-6	-134:00	18:00	Ambulatory visit, rifampicin administration							x	
				-110:00	18:00	Ambulatory visit, rifampicin administration						x	
				-86:00	18:00	Ambulatory visit, rifampicin administration						x	
				-62:00	18:00	Ambulatory visit, rifampicin administration		x 				x	
		-2	-38:00	18:00	Ambulatory visit, rifampicin administration	C 	x 					x	
				-14:30	17:30	Admission to trial site 						x 	
				-14:00	18:00	Rifampicin administration		x 					
				-13:00	19:00	Dinner							
				-12:00	20:00			x					

Proprietary confidential information © 2019 Boehringer Ingelheim International GmbH or one or more of its affiliated companies

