#### 5.2.2 Vital signs

Systolic and diastolic blood pressures (BP) as well as pulse rate (PR) will be measured by a blood pressure monitor (Dinamap, ) at the times indicated in the [Flow Chart](#), after subjects have rested for at least 5 min in a supine position. All recordings should be made using the same type of blood pressure recording instrument on the same arm, if possible.

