#### **5.2.4      Electrocardiogram**

Twelve-lead ECGs (I, II, III, aVR, aVL, aVF, V1 - V6) will be recorded using a computerised electrocardiograph ( ) at the times provided in the [Flow Chart](#).

To achieve a stable heart rate at rest and to assure high quality recordings, the site personnel will be instructed to assure a relaxed and quiet environment, so that all subjects are at complete rest.

Proprietary confidential information © 2019 Boehringer Ingelheim International GmbH or one or more of its affiliated companies

All ECGs will be recorded for a 10 sec duration after subjects have rested for at least 5 min in a supine position. ECG assessment will always precede all other study procedures scheduled for the same time to avoid compromising ECG quality.

All ECGs will be stored electronically on the Muse CV Cardiology System ( ). Electrode placement will be performed according to the method of Wilson, Goldberger and Einthoven modified by Mason and Likar (hips and shoulders instead of ankles and wrists).

All locally printed ECGs will be evaluated by the investigator or a designee. Abnormal findings will be reported as AEs (during the trial) or baseline conditions (at screening) if assessed to be clinically relevant by the investigator. Any ECG abnormalities will be carefully monitored and, if necessary, the subject will be removed from the trial and will receive the appropriate medical treatment.

ECGs may be repeated for quality reasons (for instance, due to alternating current artefacts, muscle movements, or electrode dislocation) and the repeated ECG will be used for analysis. Additional (unscheduled) ECGs may be collected by the investigator for safety reasons.

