## **5.2.5      Other safety parameters**

### **5.2.5.1      Neurological examination**

At Screening and at EoTrial examination, a physical neurological examination will be performed. Upon investigator judgment, additional neurological examinations may be added at any time during the trial, for individual subjects or for the whole treatment group.

The neurological examination will include the following assessments:

- Eye movement
- Pupil size and pupil reactivity
- Reflexes
- Assessment of muscle strength
- Gait
- Romberg test
- Tremor
- Point-to-point movements
- Sensitivity

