## 6. INVESTIGATIONAL PLAN

### 6.1 VISIT SCHEDULE

Exact times of measurements outside the permitted time windows will be documented. The acceptable time windows for screening and the end of trial examination are provided in the [Flow Chart](#).

Study measurements and assessments scheduled to occur 'before' trial medication administration on Day 1 are to be performed and completed within a 3 h-period prior to the trial drug administration.

The acceptable deviation from the scheduled time for vital signs, ECG, and laboratory tests will be  $\pm$  60 min.

If scheduled in the [Flow Chart](#) at the same time as a meal, blood sampling, vital signs, and 12-lead ECG recordings have to be done first. Furthermore, if several measurements including venepuncture are scheduled for the same time, venepuncture should be the last of the measurements due to its inconvenience to the subject and possible influence on physiological parameters.

For planned blood sampling times, refer to the [Flow Chart](#). While these nominal times should be adhered to as closely as possible, the actual sampling times will be recorded and used for the determination of pharmacokinetic parameters.

For time point 34 h (planned time) after BI 894416 administration, a time window of  $\pm$  60 min will be allowed for PK blood sampling. For time point 48 h (planned time) after BI 894416 administration, a time window of  $\pm$  120 min will be allowed for PK blood sampling.

If a subject misses an appointment, it will be rescheduled if possible. The relevance of measurements outside the permitted time windows will be assessed no later than at the Report Planning Meeting.

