### 7.3.4 Safety analyses

Safety will be analysed based on the assessments described in Section [2.2.2.2](#). All treated subjects (TS, refer to Section [7.2](#)) will be included in the safety analysis. Safety analyses will be descriptive in nature and based on BI standards. No hypothesis testing is planned.

For all analyses, the treatment actually administered (= treatment at onset) to the subject will be used (any deviations from the randomised treatment will be discussed in the minutes of the Report Planning Meeting).

Treatments will be compared in a descriptive way. Tabulations of frequencies/proportions will be used to evaluate categorical (qualitative) data, and tabulations of descriptive statistics will be used to analyse continuous (quantitative) data.

Measurements (such as ECG, vital signs, or laboratory parameters) or AEs will be assigned to treatments (see Section [4.1](#)) based on the actual treatment at the planned time of the measurement or on the recorded time of AE onset (concept of treatment emergent AEs). Therefore, measurements planned or AEs recorded prior to first intake of trial medication in period 1 will be assigned to the screening period, those between treatment with BI 894416 in period 1 and first treatment with rifampicin in period 2 are attributed to the treatment interval “BI 894416 alone”, those between first treatment with rifampicin in period 2 and treatment with BI 894416 in period 2 are attributed to the treatment interval “rifampicin alone” and those occurring between treatment with BI 894416 in period 2 and the individual subject’s end of trial are attributed to the treatment interval “BI 894416 + rifampicin”. These assignments including the corresponding time intervals will be defined in detail in the TSAP. Note that AEs occurring after the last per protocol contact but entered before final database lock will be reported to Pharmacovigilance only and will not be captured in the trial database.

Additionally, further treatment intervals (analysing treatments) may be defined in the TSAP in order to provide summary statistics for time intervals, such as combined treatments, on-treatment totals, or periods without treatment effects (such as screening and follow-up intervals).

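### Does the 4-hour ban on lying down undermine the supine ECG and vital-sign readings scheduled early after dosing?

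*Protocol*

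**What the plan says.** Protocol section 4.1.4 sets a posture rule for the period after dosing: "During the first 4 h after BI 894416 administration, subjects are not allowed to lie down". It defines the limit as "no declination of the upper body of more than 45 degrees from upright posture". It makes no exception for study procedures. None appears in the diet and lifestyle restrictions (4.2.2.2), the visit schedule (6.1), the Flow Chart footnotes or the SAP.

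Section 5.2.2 has blood pressure and pulse rate taken at the Flow Chart times, "after subjects have rested for at least 5 min in a supine position". Section 5.2.4 is worded just as broadly: "All ECGs will be recorded for a 10 sec duration after subjects have rested for at least 5 min in a supine position".

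On timing, section 6.1 states: "The acceptable deviation from the scheduled time for vital signs, ECG, and laboratory tests will be" ±60 min.

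On use of the data, protocol section 7.3.4 says "Safety analyses will be descriptive in nature and based on BI standards". SAP 6.7 takes as baseline the last value before BI 894416 in each period. SAP 7.8.3 tabulates vital signs and their change from baseline by planned time point. SAP 7.8.4 has ECGs checked by the investigator, with relevant findings reported as AEs or baseline conditions. It plans no summary by time point.

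**The concern.** A supine subject is well beyond 45 degrees from upright. If ECGs and vital signs are due within 4 hours of dosing, staff cannot satisfy 4.1.4 together with 5.2.2 and 5.2.4, and the protocol gives no order of precedence.

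Two things could be at stake. First, if some post-dose readings were taken semi-upright and compared with a supine pre-dose value, the tabulated change in vital signs would mix posture with drug. If practice also differed between periods, the BI and BI+Rifa tables would not be comparable. Second, section 1.4.3.1 lists pre- and post-dose ECGs among the measures that mitigate a possible QT effect, so the conditions of those recordings should not be in doubt.

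**Working it through.** No sample size, power or model figure is involved. The check has four steps.

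**1. Are early supine readings scheduled?** The columns of the Flow Chart are displaced in the text available for review, so its rows were read in more than one way.

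- Period 1, 1:00 row. By header position it carries ECG and vital-sign marks. The urine mark in the 4:00 row sits one column too far left. If the 1:00 row is shifted to match, its marks move to neurological examination and AE questioning.
- Period 1, 2:00 row. It carries ECG and vital-sign marks under both readings. By either reading it also carries a neurological mark, which does not fit section 5.2.5.1: "At Screening and at EoTrial examination, a physical neurological examination will be performed".
- Period 2, 1:00 row. By header position it has an ECG mark but no vital-sign mark. Aligned on the PK sample, it has both.
- Period 2, 2:00 row. It has both marks under either reading, again with a neurological mark.

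An early supine reading is therefore likely, but the exact rows are not certain. A colleague with the typeset chart can settle this by looking.

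**2. Can the tolerance move the readings out of the restricted window?** The restriction runs from 0 to 4 × 60 = 240 min.

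- 1:00 reading: 60 ± 60 = 0 to 120 min, ending 240 − 120 = 120 min before the limit.
- 2:00 reading: 120 ± 60 = 60 to 180 min, ending 240 − 180 = 60 min before the limit.

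Every permitted time falls inside the window, so the conflict cannot be scheduled away.

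**3. How many occasions?** With 16 subjects:

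- One time point in one period (vital signs at 1:00, header position): 16 × 1 × 1 = 16.
- One time point in both periods: 16 × 2 × 1 = 32.
- Both time points in both periods: 16 × 2 × 2 = 64.

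The range reflects the uncertainty in step 1. It counts readings, not consequences.

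**4. What happens to the results?** Let d be the drug-related change in a vital sign and p the shift from taking the post-dose reading in a different posture from baseline. Additivity is assumed; the documents give no value for p.

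- 5.2.2 and 5.2.4 followed: posture is the same before and after dosing, p = 0, and the tabulated change is d.
- 4.1.4 followed consistently at the early readings: the change is d + p in each period. Between periods, (d_T + p) − (d_R + p) = d_T − d_R, so that comparison survives although each within-period change is off by p.
- Mixed practice between periods: both are affected.

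Only the second and third cases do harm, and both require staff to set aside the explicit instruction for taking the measurement. For ECGs there is no time-point table to distort in any of the cases.

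The primary endpoints (AUC0-∞ and Cmax) and the secondary endpoint (AUC0-tz) come from plasma concentrations. The documents give no reason for the posture rule, so no PK effect of a few minutes supine can be derived from them. The measurement instructions are the same in both periods. If they are applied alike, any common proportional effect would cancel in the T/R ratio.

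**The case for a change.** The strongest case for a change is that each rule is specific and absolute: 4.1.4 about a time window, 5.2.2 and 5.2.4 about a procedure. Reading supine as semi-recumbent would reconcile them, but the protocol does not say that. SAP 6.2 requires deviations from the protocol to be identified for all treated subjects, so on a literal reading a deviation arises at each early measurement whichever rule is followed. The ECGs also matter: section 1.4.3.1 reports a predicted mean QTcF increase of 5.9 ms (upper 90% limit 10.5 ms) at the geometric mean Cmax of the 70 mg group. One sentence would remove the doubt at almost no cost.

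The textual conflict stands, and so does the formal deviation. The consequence does not follow. The trial has one centre (SAP 6.5), so there is no variation between sites, and nothing in the documents suggests that staff would take readings otherwise than 5.2.2 and 5.2.4 direct. Posture is not among the examples of PK-relevant deviations in protocol section 7.3. That list is open, but importance is judged by the trial team at the report planning meeting, and a reading taken as its own section instructs is an unlikely reason to exclude data. For the ECGs, 5.2.4 already fixes the recording conditions.

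**Conclusion.** The point is a missing procedural exception in the wording, not a flaw in the design or analysis. The three sections do not fit together as written, and the tolerance in 6.1 does not reconcile them. But the measurement sections tell staff how to take each reading, and on that basis baseline and post-dose posture agree, the descriptive vital-sign tables are interpretable, and the ECG safety check is unaffected. No effect on the PK endpoints, the mixed model or the precision calculation is shown. A clarifying sentence would record how the rules fit together without altering any result or conclusion.

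The size is 16 to 64 formal departures from 4.1.4, depending on how the Flow Chart is read, with no expected shift in any tabulated result. This assumes that staff follow 5.2.2 and 5.2.4 and do so alike in both periods. If early readings were in fact taken in another posture, the vital-sign changes at those time points would need a caveat in the report. This note takes no position on which posture rule should prevail. If the protocol is amended for another reason, 4.1.4, 5.2.2 and 5.2.4 can be reconciled then.

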#### **4.1.5 Blinding and procedures for unblinding**

This Phase I trial will be handled in an open fashion throughout (that is, during the conduct, including data cleaning and preparation of the analysis). This is considered acceptable because the potential for bias seems to be low and does not outweigh practical considerations.

Emergency envelopes will not be provided, because the dose of trial medication is known to investigators and subjects.

